**2/2/2024**

## 1. Introduction

Peri-implant mucositis (PM) is a highly prevalent disease characterized by inflammation of the peri-implant mucosa without loss of the supporting bone (Berglundh, Armitage, et al., 2018; Ferreira et al., 2006; Koldsland et al., 2010; Romandini et al., 2019; Romandini, Lima, et al., 2021; Wada et al., 2019). Its main clinical sign is the presence of bleeding on (gentle) probing (BoP) (Berglundh, Armitage, et al., 2018). If untreated, PM may progress into peri-implantitis, which is further characterized by the loss of supporting bone and may ultimately lead to implant loss (Costa et al., 2012; Derkx et al., 2016).

Similarly to the etiology of periodontal diseases, multiple clinical studies have described a cause-effect relationship between the accumulation of experimental plaque and the development of PM (Pontoriero et al., 1994; Zitzmann et al., 2001). However, soft tissues around implants develop a stronger inflammatory response to experimental plaque buildup when compared to inflammation developed around teeth (gingivitis) (Salvi et al., 2012).

The treatment of PM is focused on the disruption of the dental implant biofilm and aimed at achieving treatment success/disease resolution (i.e., absence of BoP), or at least a reduction in the number of bleeding sites (i.e., BoP extent) or of its severity (e.g., modified bleeding index or mBI; Mombelli et al., 1987; Renvert et al., 2018). Therefore, after a patient's behavioural phase including oral hygiene instructions (OHI), the affected implants usually undergo non-surgical instrumentation, which may be realized through mechanical (e.g., curettes, ultrasonics, air-polishing) and/or physical (e.g., laser) approaches (Baima et al., 2022; Renvert et al., 2019). Adjunctive measures (e.g., antiseptics) may also be used (Jepsen et al., 2015). Many studies have shown that non-surgical mechanical treatment can successfully control PM, reducing plaque and bleeding scores (Renvert et al., 2008).

As mentioned before, the occurrence of PM is mainly influenced by plaque accumulation and therefore effective oral hygiene practices are fundamental in their prevention and management. In fact, there is evidence from experimental human studies that PM resolution may occur with adequate biofilm control (Meyer et al., 2017; Salvi et al., 2012; Schincaglia et al., 2017). The reversibility of experimental PM after the re-institution of plaque control has been confirmed by the decrease to baseline values of crevicular fluid levels of host-derived biomarkers (Salvi et al., 2012). And as it was stated in the latest expert consensus on the prevention and treatment of peri-implant diseases (Herrera et al., 2023), even though, the traditional treatment of PM includes mechanical professional cleaning, up to date the added benefit of professional mechanical/physical instrumentation as compared to OHI alone is not known.

It is therefore the aim of this randomized clinical trial to identify if there is any superiority of mechanical/physical instrumentation over OHI alone.

## 2. Objectives

### **-Primary objective:**

Evaluate the resolution of the disease, by means of reduction of modified bleeding index (mBI), by individualized OHI and proper oral hygiene measures conducted by the patient after 1 and 3 months of protocol instauration in comparison to the combination of individualized OHI and professional mechanical debridement.

### **-Secondary objectives:**

- Evaluate microbiological changes by individualized OHI and proper oral hygiene measures conducted by the patient after 1 and 3 months of protocol instauration in comparison to the combination of individualized OHI and professional mechanical debridement.
- Determine if the extent of inflammation measured as the initial mBI could have any impact in the PM resolution after treatment.

## 3. Hypothesis

- The proper oral hygiene measures conducted by the patient after individualized OHI will achieve resolution of PM in a clinically relevant proportion of patients.
- The proper oral hygiene measures conducted by the patient after individualized OHI will reduce the expression of peri-implant pathogens as much as the combination of individualized OHI and professional mechanical debridement in a clinically relevant proportion of patients.
- The proper oral hygiene measures conducted by the patient after individualized OHI will reduce mBI as much as the combination of individualized OHI and professional mechanical debridement in a clinically relevant proportion of patients.
- The extent of inflammation measured as the mBI could be related with the degree of resolution of the disease according to the treatment.

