### **Clinical, radiographic and microbiological examination**

At baseline, 1 (1m) and 3 months (3m) after treatment, two calibrated examiners ([name] and [name]) will record the following clinical variables using an electronic, pressure-calibrated probe (PA\_ON Probe, Orange Dental®, [name], Biberach, Germany), with a standardized probing force of 0.20 N.

At the full-mouth level, the following parameters will be evaluated:

- (1) Full mouth plaque Index (FMPI), assessed dichotomously at four sites per tooth (mesial, buccal, distal, and lingual).
- (2) Full mouth bleeding index (FMBI), assessed dichotomously as presence or absence of bleeding after 30 seconds of gently probing (Ainamo and Bay, 1975).
- (3) Full mouth probing pocket depth (FMPPD), measured at six sites around each tooth, except third molars.

At local level, in six sites around each implant, the following clinical variables will be recorded:

- (1) Modified plaque index (mPI) (Mombelli et al., 1987)
- (2) Modified bleeding index (mBI) (Mombelli et al., 1987), dichotomized in presence/absence of bleeding and selected as the primary outcome (BOP).
- (3) Suppuration on probing (SOP), assessed dichotomously as presence or absence of suppuration within 30 seconds after probing.
- (4) Implant probing pocket depth (PPDi), measured from the mucosal margin to the bottom of the probable pocket.
- (5) Implant mucosal recession (MRI), measured from the implant neck to the mucosal margin.

Disease resolution will be considered when a mBI <0.16 is achieved, as it was established in the last consensus performed to develop the clinical practice guidelines on the treatment of peri-implant diseases (Herrera et al. 2023).

Individual acrylic resin occlusal stents, exhibiting six vertical grooves per implant (mesiobuccal, midbuccal, distobuccal, mesiolingual, midlingual and distolingual), will be built in order to allow a reproducible direction and angulation during probing.

A periapical radiograph of all implants involved in the study will be taken using a paralleling cone technique and a film-holder (7mA- 60kV/20ms) at baseline and at 3 months after treatment, in order to detect any loss of supporting bone.

Furthermore, sampling for microbiological test will be conducted at baseline, 1m and 3months after treatment.

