## **SAMPLE SIZE CALCULATION**

The unit of analysis will be set at the patient. In those patients with more than one implant fulfilling the inclusion criteria, a mean of the implants included will be taken into consideration for the analysis. Sample size was calculated according to the main outcome “complete disease resolution”. Taking into account that previous studies showed a disease resolution around 66.6% (de Tapia et al. 2019) after treatment by means OHI and mechanical debridement, we estimate that at least 50% of patients receiving OHI as a single therapy could present a complete resolution. Accepting an alpha risk of 5% and a beta risk of 10% in a two-sided test, 28 subjects are necessary. It has been anticipated a drop-out rate of 15%. In order to include a second group of patients receiving an usual management as control group, we will include a total of 56 patients (28 in each group).

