## **5. Results analysis**

The data contained in the CRFs will be entered into a database for data analysis and preparation of the final report.

The socio-demographic and clinical characteristics and other variables of interest of the patients included in the study will be described. Data will be presented as mean  $\pm$  SD; categorical data will be shown as percentage of positive patients.

The relationship between two qualitative variables will be calculated using the chi-squared test or Fisher's exact test (frequency  $< 5$ )

For ordinal variables, linear regression will be calculated using Kendall's tau coefficient.

Quantitative variables will be compared using the Student's t-test (< 2 categories), analysis of variance [ANOVA] (> 2 categories), linear regression test and Scheffé's multiple comparisons test or U Mann Whitney.

The linear relationship between the quantitative variables will be calculated using Pearson's correlation coefficient or Spearman's rank correlation test (when variable not normally distributed).

Changes *versus* baseline will be analyzed by Wilcoxon non-parametric test or Mc Nemar test.

A logistic regression model will be set in order to determine whether the initial extent of the inflammation, mBI, is related to disease resolution

Level of significance will be set at 0.05. The SPSS version 19.00 software (SPSS Inc., Chicago, IL, USA) will be used for all analyses.

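### Two of the four hypotheses say OHI alone works as well as OHI plus debridement, but the planned difference tests cannot confirm either one

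*Combined protocol and SAP*

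**What the plan says.** Section 3 (Hypothesis) lists four statements, and two of them compare the arms in equal-effect terms. The second says that OHI alone "will reduce the expression of peri-implant pathogens as much as the combination of individualized OHI and professional mechanical debridement". The third says that it "will reduce mBI as much as the combination of individualized OHI and professional mechanical debridement in a clinically relevant proportion of patients". The first (resolution with OHI) and the fourth (baseline extent of inflammation) make no such claim and are outside this point.

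The Introduction gives the aim in the other direction: to "identify if there is any superiority of mechanical/physical instrumentation over OHI alone". The objectives in section 2 are neutral comparisons. The primary one evaluates mBI reduction "after 1 and 3 months of protocol instauration in comparison to the combination of individualized OHI and professional mechanical debridement"; the first secondary one is to "Evaluate microbiological changes by individualized OHI and proper oral hygiene measures conducted by the patient after 1 and 3 months".

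The sample size section assumes 66.6% resolution with OHI plus debridement and at least 50% with OHI alone, and states: "Accepting an alpha risk of 5% and a beta risk of 10% in a two-sided test, 28 subjects are necessary". The examination section has mBI "dichotomized in presence/absence of bleeding and selected as the primary outcome (BOP").

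Section 5 (Results analysis) opens its list of tests with "The relationship between two qualitative variables will be calculated using the chi-squared test" or Fisher's exact test for small frequencies. It adds t-test, ANOVA, regression or Mann-Whitney for quantitative variables, correlations, Wilcoxon or McNemar for change from baseline, and a logistic model. Results are to be presented as means with SD and as percentages.

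**The concern.** A test of difference has two outcomes: it rejects equality or it fails to reject it. Neither shows that one treatment does as much as another. That would need a margin, fixed in advance, and a confidence interval or equivalent test that excludes differences beyond it. The protocol has none of these, and does not say how p>0.05 will be read.

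The Introduction says the added benefit of professional instrumentation over OHI alone is unknown. If a non-significant comparison is taken as confirming the second and third hypotheses, the trial will appear to have answered that question in the negative while its data remain compatible with a material benefit. The mBI hypothesis carries most weight, because mBI reduction is the measure in the primary objective.

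**Working it through.** **1. Hypotheses set against analyses.**

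| Element | Where | What it is |
|---|---|---|
| Aim | Introduction | Superiority of instrumentation |
| Sizing | Sample size calculation | Two-sided test, 66.6% versus 50% |
| Hypotheses 2 and 3 | Section 3 | Equal effect of OHI alone |
| Tests | Section 5 | Difference, association, change; 0.05 level |
| Margin, between-group CI, rule for p>0.05 | Nowhere | None |

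Aim, sizing and tests fit one another; hypotheses 2 and 3 do not fit them. The closing qualifier about a clinically relevant proportion of patients cannot serve as a margin. Read as a share of patients, it gives neither the share nor a rule for when one patient's reduction counts as equal.

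**2. The plan's own figure.** Inputs from the sample size section: p1 = 0.666, p2 = 0.50, alpha 0.05 two-sided, power 90%, 15% drop-out, 28 per group. The usual two-group formula, with mean rate 0.583, gives

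n = [1.960·√(2·0.583·0.417) + 1.282·√(0.666·0.334 + 0.50·0.50)]² / 0.166² = 183.3, so 184 per group.

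The stated 28 is not reproduced. That is a separate defect in the sample size section and is not counted here; the present point would stand at any n.

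**3. How often p>0.05 arises, binary resolution.** Exact enumeration of all outcomes at 0.666 versus 0.50:

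| Per group | Chi-squared power | P(p>0.05) | Fisher power | P(p>0.05) |
|---|---|---|---|---|
| 28 | 0.233 | 0.767 | 0.162 | 0.838 |
| 24 (28 × 0.85 = 23.8) | 0.231 | 0.769 | 0.150 | 0.850 |

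The smallest expected cell is 28 × (1 − 0.583) = 11.7, so under section 5 chi-squared is the applicable test and 77% the relevant figure. Large effects would be found more often: if OHI resolution were 40% or 30% (my assumption), chi-squared power at 28 per group is 50% or 79%.

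**4. What a CI would show.** Half-width = 1.96·√[(0.666·0.334 + 0.25)/n]:

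- n = 28: 0.255
- n = 24: 0.275

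An observed gap of 0.166 at 28 per group gives 0.166 ± 0.255, or −0.089 to 0.421.

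**5. mBI score and pathogens.** The documents give no SD or expected difference, so the chance of p>0.05 cannot be derived. The precision of a mean difference can be given in SD units, t(0.975, 2n−2)·√(2/n):

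- n = 28: 2.005 × 0.267 = 0.54 SD
- n = 24: 2.013 × 0.289 = 0.58 SD

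**6. What an equal-effect claim would need.** Assume both true rates are 66.6% and use one-sided 0.025. The margin supported by 28 per group is (1.960 + z)·√(2·0.666·0.334/28):

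- 80% power: 2.802 × 0.126 = 0.353
- 90% power: 3.242 × 0.126 = 0.409

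For a 20-point margin (my assumption) at 90% power: n = 3.242²·2·0.666·0.334/0.20² = 116.9, so 117 evaluable per group.

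**The case against.** The strongest reply is that this is a superiority trial with two loosely worded bullets. Aim, objectives, sizing and tests agree, the bullets may be only expectations, and nothing in the protocol says that p>0.05 will be read as equality. It is true that the rest of the plan is coherent and that the harm depends on a later misreading. But the bullets stand in the protocol's Hypothesis section, nothing planned can confirm them, and the silence on p>0.05 leaves the misreading open.

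The qualifier could be read as a responder-type statement. On that reading the fault is an undefined threshold, and the hypotheses still cannot be tested as written.

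The binary power figures concern resolution, which is directly the outcome of hypothesis 1. This stands in part: dichotomised mBI links them to hypothesis 3, but nothing links them to pathogens. Only the SD-unit half-widths apply to a mean difference in either measure.

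The advice against non-inferiority depends on 28 per group. This stands. If the sample size were corrected to 184 per group, the formula in step 6 would support a margin of 3.242·√(2·0.666·0.334/184) = 0.159 at 90% power, and the sponsor could revisit the choice.

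Finally, no microbiological scale is named, so a CI for pathogens first needs an endpoint. That is correct, but any pathogen test under section 5 needs one too.

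**Conclusion.** The concern holds. Hypotheses 2 and 3 claim equal effect, and no analysis in section 5 can confirm either, whatever the sample size. The fault is a mismatch between hypothesis and analysis, and it should be corrected; it does not undermine the superiority comparison itself.

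Its practical size is firm only for binary resolution: at the protocol's planning rates, a non-significant chi-squared result is expected about 77% of the time despite a true 16.6-point deficit. For mBI score and pathogens only relative precision can be stated, and that assumes a continuous measure compared by means. The margin figures rest on equal true rates of 66.6%; the 20-point margin is illustrative, since the documents give none.

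**What to change.** 1. **Section 3, second and third hypotheses.** Replace the equal-effect wording with a question that matches the Introduction, for example: *The difference in mBI reduction (and in pathogen reduction) between OHI plus debridement and OHI alone will be estimated, and superiority of the combination tested.*
2. **Section 5, estimates.** Add the between-group difference (control minus test) with a two-sided 95% CI for resolution, mBI and pathogens at 1 and 3 months. Name the scale of the microbiological measure so that its difference can be computed.
3. **Section 5, interpretation.** Add: *A p-value above 0.05 will not be interpreted as equal effect; conclusions will be based on the confidence interval.*
4. **No non-inferiority or equivalence claim at 28 per group.**

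The cost is wording, one CI per comparison and a stated pathogen scale, with no extra patients, visits or data. The sponsor loses the option of claiming equal effect from a non-significant result. Keeping that claim would need a justified margin and a larger trial: about 117 evaluable per group for the illustrative 20-point margin, against 28 planned.

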## 4. Material and methods

### **ETHICAL ISSUES**

This study will be performed according to the principles outlined in the Declaration of Helsinki and Ethical Conduct for Research with Human Beings and after the approval of the Ethics Committee of the Universitat Internacional de Catalunya (UIC).

## **STUDY DESIGN**

The present study will be a prospective randomized controlled intervention trial with a 3-month follow-up.

Randomization of patients will be performed using a computer-generated list with permuted blocks of four. Allocation concealment will be assured by using sealed opaque envelopes that assigned patients to their respective treatment groups. These envelopes will be labelled with the patient study number and only open once after patient has received OH

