## **STUDY POPULATION**

Patients attending to the Department of Periodontology at UIC and diagnosed with PM will be recruited consecutively. One calibrated investigator ([name]) will evaluate patients for screening and will be responsible of enrolling them in the study if they fulfilled the following inclusion and exclusion criteria.

Inclusion criteria:

- (1) Presence of, at least, one titanium implant that have been more than one year in function and exhibits PM, defined as bleeding on gentle probing (0.20 N) in at least one peri-implant site.
- (2) No signs of loss of supporting bone after initial bone remodelling. In cases where baseline radiograph is available, it will be used for comparison, otherwise a maximum of 2 mm of crestal bone loss will be accepted (Sanz et al. 2012).
- (3) Presence of >1 mm of keratinized peri-implant mucosa.
- (4) Absence of systemic diseases that could influence the outcome of the therapy (i.e. controlled diabetes, with HbA1c<7, patients will be included).
- (5) Non-smoker or light smoking status in smokers (<10 cigarettes/day).

Patients will be excluded if:

- (1) Untreated periodontal conditions.
- (2) Pregnant or lactating women.
- (3) Patients who received systemic antibiotics in the last 3 months.
- (4) Patients who received treatment of PM in the past 3 months.

(5) Patients receiving corticoids or medications known to have effect on gingival growth (i.e., calcium channel antagonists, immunosuppressants or antiepileptic drugs).

In those cases diagnosed with peri-implantitis, individualized treatment will be provided, apart from the present study.

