## **TREATMENT**

All patients (test and control) will be instructed to brush the implants twice daily to remove supragingival biofilms with a low-abrasive dentifrice and to use specific cylindrical or conical brushes (Interprox®, Dentaid, Barcelona, Spain) in the interproximal area. Patients will be indicated to brush under, around, and in the peri-implant crevice circumferentially. In those cases with no access for proper OHI, prosthesis will be modified according to the protocol described by de Tapia et al. 2019. The interproximal brush device used will be chosen for the patient individually, according to the interproximal space available, the thicker brush that can be used comfortably will be the selected one. It will be previously tested on the patient and its use will be taught, patients should demonstrate proficiency.

- Control group: On the affected implants, supra- and sub-gingival debridement of the implant surface, the implant neck, and the abutment will be carried out by means of a combination of ultrasonics (DTE-D5, Woodpecker®, Guilin, China) with a plastic tip (Hu-Friedy®, [name], Chicago, IL, USA) and plastic curettes (Hu-Friedy®). Finally, the prosthetic components will be polished with a rubber cup.
- Test group: No further treatment will be provided.

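### Fixed blocks of four in a single-centre trial with visibly different arms could let up to one third of allocations be deduced before oral hygiene instruction is given

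*Combined protocol and SAP*

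**What the plan says.** STUDY DESIGN specifies a "computer-generated list with permuted blocks of four". It names no second block size, no random variation in size and no stratification. On concealment it states: "Allocation concealment will be assured by using sealed opaque envelopes that assigned patients to their respective treatment groups". The envelopes carry the patient study number and are "only open once after patient has received OH". The available text of that sentence stops there; I read it as meaning after OHI.

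STUDY POPULATION describes one department with consecutive recruitment, and one investigator who "will evaluate patients for screening and will be responsible of enrolling them in the study".

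TREATMENT gives both arms the same OHI. The interproximal brush is chosen for each patient, the prosthesis may be modified for access, and "patients should demonstrate proficiency". The control arm then has ultrasonic and curette debridement and polishing. The test arm has nothing more, and no sham is described. Annex 1 places screening and treatment in the same visit.

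SAMPLE SIZE CALCULATION gives the total: "we will include a total of 56 patients (28 in each group").

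The documents do not say who delivers OHI, who opens the envelopes or who debrides. They describe no step that hides the block size or earlier allocations from those people.

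**The concern.** A sealed envelope hides the paper. It does not hide what can be worked out from the patients already treated. When every block holds two of each arm and the size is known, the last allocation in a block always follows from the first three, and sometimes the third follows from the first two. Because treatment is given at the screening visit and differs visibly, an earlier allocation will normally have been acted on before the next patient is enrolled.

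The point matters here because of the order of events. OHI is the whole of the test treatment and the common background of the control. Opening the envelope only after OHI is the plan's safeguard for equal OHI in both arms, and it works only if the arm cannot be deduced beforehand. OHI delivery involves judgement, and the proficiency requirement has no stated criterion. An instructor who expects a patient to receive OHI alone could teach longer or ask for more before accepting proficiency. That could narrow the difference between arms, in the direction of the hypothesis in section 3 that OHI alone reduces the bleeding index as much as the combination.

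**Working it through.** **Inputs.** Block size 4 (STUDY DESIGN). Total 56, allocated 28 and 28 (SAMPLE SIZE CALCULATION), so 56 / 4 = 14 complete blocks. The documents give no figure for predictability, so there is none to reproduce.

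**Assumption.** The observer knows the block size and every earlier allocation.

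**Allocations known with certainty, fixed blocks of four.** There are six equally likely orders of two A and two B. An allocation is certain once both places of one arm are used.
- Positions 1 and 2: never certain.
- Position 3: certain when the first two are alike (AA or BB), which is 2 of 6 orders, or 1/3.
- Position 4: always certain.
- Per block: 1/3 + 1 = 4/3. As a share: (4/3) / 4 = 33.3%.
- Over the trial: 14 × 4/3 = 18.7 of 56. The number is 14 plus a binomial count (14 blocks, probability 1/3), with a central 95% range of about 15 to 22.

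**Best guessing, fixed blocks of four.** The observer guesses the arm with more places left and tosses a coin when they are equal.
- Position 1: 1/2.
- Position 2: 2/3.
- Position 3: 1/3 × 1 + 2/3 × 1/2 = 2/3.
- Position 4: 1.
- Average: (1/2 + 2/3 + 2/3 + 1) / 4 = 70.8%. Guessing without information gives 50%.

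**Randomly varying sizes.** I used simulation: 4,000 lists of 56, with each size equally likely. The observer knows the set of sizes and all earlier allocations and updates by Bayes' rule.

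| Block sizes | Certain | Best guess correct |
|---|---|---|
| 4, fixed | 33.3% | 70.8% |
| 4 and 6 | about 5.7% | about 69% |
| 4, 6 and 8 | about 2.4% | about 68% |

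With sizes 4 and 6, about 0.057 × 56 = 3 allocations are certain, against about 19. Certainty falls because two alike at the start of a block no longer settle the third: the block may be a six. The guessing advantage hardly moves, because the arm that is behind remains the better bet.

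**Imbalance at the end.** With fixed fours, 56 is 14 complete blocks, so the difference is 0. With sizes 4 and 6, every block ends at an even number. Patient 56 therefore either completes a block or stands at position 2 or 4 within one. At position 2 the largest difference is 2 − 0 = 2. At position 4 of a six it is 3 − 1 = 2. The maximum at 56 is therefore 2. A difference of 3 needs three alike at position 3 of a six, which requires recruitment to stop at an odd number.

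**The case against.** The strongest reply is that the one-third figure depends on a condition the documents do not establish. It needs someone who knows the block size, sees every earlier allocation and keeps a tally. The protocol gives one investigator screening and enrolment, but does not say that this person sees allocations or teaches OHI. If whoever enrols and whoever teaches are unaware of earlier allocations, the share falls, possibly to 0. This stands, and it makes one third an upper limit. A reader might infer that the enrolling team does know a third of allocations in advance; the text does not support that.

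There are safeguards too. The plan says: "Patients attending to the Department of Periodontology at UIC and diagnosed with PM will be recruited consecutively". With listed eligibility criteria, this limits delaying or selecting patients, so selective enrolment is the weaker route. It does not limit unequal OHI effort. TREATMENT applies the same OHI steps and proficiency requirement to both arms, but without a threshold this is only partial protection. The envelope is already opened after OHI, so a request for that order alone would add nothing.

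It is also fair to say that varying the block size removes certainty but little of the guessing advantage. This stands, and it is why the fix cannot rest on block size alone.

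**Conclusion.** The weakness holds in conditional form. Up to one third of allocations, about 19 of 56, could be deduced with certainty, and about 71% could be guessed correctly, by someone who knows the block size and sees earlier allocations. The protocol discloses the size and describes nothing that keeps earlier allocations from those who enrol or instruct. Opening the envelope after OHI therefore does not fully protect against unequal OHI effort.

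The conclusion rests on three readings: that the truncated envelope sentence means after OHI; that the block size is fixed, since no other is mentioned; and that OHI depends on the person giving it, which I infer from its individual tailoring.

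A reader might go further and conclude that the comparison is biased. The documents do not support that. The figures measure predictability, not its effect on resolution rates, and no size of bias can be derived. This is a design weakness with a cheap remedy, not a fatal flaw.

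**What to change.** 1. In STUDY DESIGN, replace the fixed size with permuted blocks of randomly varying size, and do not print the sizes there. Hold the sizes (for example 4 and 6) and the list in a restricted document unavailable to those who enrol, instruct or treat.
2. Where existing staffing allows, keep the person giving OHI unaware of earlier allocations. This addresses the guessing advantage, which varying the block size leaves almost intact.
3. Record completion of OHI and of the proficiency check before the envelope is opened. The opening order is already in the plan; the record is new.

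The cost is a regenerated list (or its unused part), a sentence or two of protocol text, a restricted document and one entry in the case report form. With sizes 4 and 6, the maximum imbalance at 56 patients rises from 0 to 2, and 3 is possible only if recruitment stops at an odd number. Item 2 may need a separation of roles, which is why it depends on staffing.
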